Study Protocol – Version 5, March 30, 2023

NCT05503823

Project Title: Investigating Transcranial Alternating Current Stimulation (tACS) Preconditioning Effects on Resting and Active Motor Threshold

1. Summary of the Project

Transcranial Magnetic Stimulation (TMS) is a non-invasive brain stimulation technique which uses a large and rapidly changing magnetic field pulse for stimulation. Exposure to TMS has been associated with the improvement of the brain's plasticity and memory loss [1]. These after-effects of TMS are temporal and short-term. However, repetitive sessions of preconditioning the brain before TMS has the potential to extend the duration of these after-effects while also reducing the amount of exposure necessary for observable results. The proposed study focuses on providing some insight on the effects of priming the brain via Transcranial Alternating Current Stimulation (tACS) and Transcranial Random Noise Stimulation (tRNS) before applying TMS.

In this study, single pulse TMS is applied over the primary motor cortex, specifically for the hand area to find the resting and active motor thresholds. The Resting Motor Threshold (RMT) is the lowest intensity to produce involuntary hand twitches while the hand is at a relaxed position or when the motor evoked potential has a peak-to-peak amplitude of greater than $50\mu\text{V}$ for 5 of 10 trials [2][3]. The active motor threshold (AMT) is similarly the lowest intensity at which the participant shows involuntary hand twitches, but this time while the hand is contracted. AMT is also measured similarly as the lowest intensity at which the motor evoked potential has a peak-to-peak amplitude of greater than $100\mu\text{V}$ for 5 of 10 trials [4][5]. The electromyography (EMG) of the First Dorsal Interosseous muscle (FDI) is recorded before the application of tACS as a baseline for both RMT and AMT. Then the tACS/tRNS is applied at 40Hz for 10 minutes with the active electrode over the exact location of the TMS application (the hand area of the primary motor cortex) and the reference over the right supraorbital area. Then the EMG is recorded immediately after tACS/tRNS, 30 minutes after, and 1 hour after exposure to tACS/tRNS. These recordings are done both in resting and active states of the muscle. The objective is to observe a change in the motor evoked potentials (MEPs) after exposure to tACS or tRNS and analyze the time of the sustained MEP change.

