Motor Evoked Potential (MEP)

Motor evoked potential, as shown in Figure 1, is the involuntary response of the muscle due to the magnetic stimulation to the corresponding area of the brain, hand area for the primary motor cortex. In this study, we are collecting the FDI (first dorsal interosseous) EMG to observe the change in the peak-to-peak value of the MEP. A noticeable increase in the peak-to-peak value of the MEP, while a constant amount of TMS intensity is applied to the brain before and after priming via tACS/tRNS is used, suggests that the priming has been in fact successful, and the motor threshold has been reduced due to the priming.

The EMG recorded before and after tACS/tRNS will be compared to observe any change in the MEP.

[figure not shown]

Figure 1. Active FDI EMG with MEP and cSP

Cortical Silent Period (cSP)

Cortical silent period (cSP) refers to the silent period that is followed immediately after MEP. This period is only observable in an active muscle EMG. By measuring the duration of cSP we can estimate the intracortical inhibition of pyramidal neurons caused by activation of GABA_B (gamma-aminobutyric acids) [8]. A noticeable decrease in the cSP potentially indicates that the preconditioning stimulation via tACS/tRNS has been effective. In this study we will be collecting the active muscle EMG during TMS sessions before and after application of tACS/tRNS.

7. Informed Consent

A consent form will be provided to the volunteers at the beginning of the two-hour session to inform them about the requirements of the study, risks and benefits, withdrawal process, confidentiality policies, and debriefing procedure. The volunteers who wish to participate in the

study will sign the consent form and will be provided with a copy of the form for safekeeping. The original form will be locked along with the participants assigned code in a locked cabinet in the research supervisor's office.

8. Procedure

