All volunteers will be contacted by the research assistant (RA) via phone or email. The RA will briefly explain the study while also setting a time slot for the volunteers to come in and read the consent form and discuss it. If the participant wishes to continue the study and signs the consent form, the RA can start the initial assessments by taking the MoCA test and having the participant fill out the questionnaire. Once the volunteers meet the criteria of the study, they will be assigned a code and enrolled to the study and all their data will be recorded under the assigned code. The consent forms which contain the participants code and contact information will be locked in a cabinet in the PI's office.

Once enrolled, participants will be examined to achieve their RMT (resting motor threshold). To do this, first the Vicra camera is turned on and the scalp of the participant is measured and saved on the computer. Then single TMS pulses are applied with the coil positioned over the right-hand area of the primary motor cortex on the left hemisphere (C3) with initial intensity of 50% of the maximum intensity. The coil position will be adjusted over the primary motor cortex until the "hotspot" is found and an involuntary right-thumb twitch is observed. If no twitch was observed after few pulses, the intensity will be increased by increments of 5% until the hotspot is found. Once the "hotspot" is found, it will be marked as a target using the coordinating camera and the intensity will be reduced by decrements of 1% to the minimum intensity where a twitch is observed. The coordinating camera will be used to record the exact position and direction of the coil while a hotspot was achieved to help us accurately stimulate the hotspot once it is found. Similar procedure is applied to determine RMT for the right side of the brain, i.e. left hand movement.

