Once the minimum intensity is recorded for the RMT, the participant gets a 10-minute break from the stimulation. During this time, the RA will measure the blood pressure and oxygen level and connect the electrodes over the FDI muscle of the right hand to record EMG and prepare the participant for the TMS session. During the first TMS session, 10 single pulses are applied to the participant over the hotspot recorded by the coordinating camera. The resting EMG of the corresponding muscle in a relaxed position will be recorded for further investigation under the participant code name. Immediately after, the participant will be asked to gently hold the arm rest of the chair and the active EMG will be recorded over 10 single pulses of TMS.

The participant will be given a 5-minute break, during which the RA place the tACS active electrode on the hotspot marked by the coordinating camera and the reference on the contralateral motor cortex. When the electrodes are all set up, tACS will be applied gradually from lower current intensity to higher for 1 minute to allow the participant to adjust to the current. The current is applied at 40 Hz frequency for the duration of 10 minutes. Immediately after the application of tACS the participant's resting and active EMG will be recorded similar to the pre-tACS procedure, with 10 pulses of TMS for each of the resting and active experiments.

Also, the blood pressure and oxygen level will be remeasured. A similar procedure will be followed to record the resting and active EMG after 30 minutes and after 1 hour from the initial application of tACS.

During the second session, the participant will be monitored by the exclusion questionnaire. If the participant passes the criteria, the RMT will be measured again and a similar procedure to the first session will be followed while tRNS is used instead of tACS. The second session can begin after 4 hours following the first session and may occur on a separate day depending on the participant's availability.

Each of these procedures will be applied once on each participant and the experiment for each participant will be done after one or two visits to the laboratory.

Data collection for the study will take place for a period of one year.

All the data will be deleted and destroyed 3 years after completion of the study.

9. Deception

There is no deception in this study.

10. Feedback/Debriefing

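### The coil site and resting motor threshold are fixed by a visible twitch before the FDI electrodes go on, and are never checked against the FDI response that supplies every EMG outcome

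*Combined protocol and SAP*

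**What the plan says.** **Search (Section 8, Procedure).** The coil is moved over the left motor cortex until the hotspot "is found and an involuntary right-thumb twitch is observed". The position is saved as a target, and then "the intensity will be reduced by decrements of 1% to the minimum intensity where a twitch is observed". No number of pulses per step is given, no microvolt criterion is used, and FDI is not mentioned at this stage.

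**Electrodes (Section 8).** "Once the minimum intensity is recorded for the RMT, the participant gets a 10-minute break from the stimulation". In that break the research assistant is to "connect the electrodes over the FDI muscle of the right hand to record EMG".

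**Recording (Section 8).** "10 single pulses are applied to the participant over the hotspot recorded by the coordinating camera", first at rest and then with the hand active. The active tACS electrode is placed on the same saved hotspot. In session 2 the RMT is measured again and a similar procedure is followed with tRNS.

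**Definitions (Section 1).** RMT may be defined in either of two ways: the lowest intensity giving a hand twitch at rest, or the EMG rule of more than 50 microvolts in 5 of 10 trials. The FDI EMG "is recorded before the application of tACS as a baseline for both RMT and AMT".

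**Outcomes (Section 6, Data Analysis).** MEP peak-to-peak amplitude and cortical silent period (cSP) are both read from the FDI recording. MEPs are compared "while a constant amount of TMS intensity is applied to the brain before and after priming". Neither the value of that intensity nor its relation to RMT is stated.

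**The concern.** The study asks whether tACS or tRNS changes the FDI response and, through it, the motor threshold. The two settings that govern the size of that response are where the coil sits and how strong the pulse is. The site is chosen without reference to FDI. The only threshold the protocol determines is also chosen that way. If they suit FDI poorly in some participants, the baseline FDI response in those people sits at an uncontrolled point on its response curve. A very small baseline leaves little room to show a fall, and uneven baselines add between-person variability.

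Two inferences are also at stake. Section 6 reads a rise in MEP as a reduction in motor threshold, which is harder to defend when the threshold was never determined in the measured muscle. Since RMT is found afresh in session 2, any search error can also differ between the tACS and tRNS sessions.

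**Working it through.** The plan gives no figure for this point, so there is none to reproduce. The check is mainly one of sequence.

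**1. Order of steps in session 1 (Section 8)**

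| Step | Criterion or action | FDI EMG available? |
|---|---|---|
| Find hotspot | visible right-thumb twitch | no |
| Set RMT | lowest level with a visible twitch, 1% steps | no |
| 10-minute break | FDI electrodes attached | from here on |
| 10 resting and 10 active pulses | at the saved hotspot | yes |
| tACS | active electrode on the saved hotspot | – |
| Immediately after, 30 minutes, 1 hour | same recordings | yes |

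The EMG definition in Section 1 needs an MEP, and no EMG is connected while the threshold is being sought. So only the twitch definition can be applied. After the electrodes are on, no step re-tests the site or the level.

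**2. Does another section fill the gap?** Section 3 says EMG is recorded during all TMS sessions. Section 8, however, uses the term first TMS session for the 10-pulse block that follows the RMT search, so the statement does not reach back to the search.

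**3. How much is left open about FDI? (illustration)** Let p be the chance that one pulse at the twitch-set level gives an FDI MEP above 50 microvolts. The documents give no value for p, so a range is assumed. The chance of meeting the Section 1 EMG rule is

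P(X ≥ 5), X ~ Binomial(10, p).

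| Assumed p | Chance that 5 of 10 is met |
|---|---|
| 0.2 | 0.033 |
| 0.4 | 0.37 |
| 0.5 | 0.62 |
| 0.6 | 0.83 |
| 0.7 | 0.95 |
| 0.8 | 0.994 |

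The twitch-set level could therefore be well below, at, or well above the FDI threshold, and the protocol has no step that shows which. The table does not say which values of p are likely.

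**4. A separate point: the pulse count.** Section 8 does not say how many pulses are judged at each level. Take a level at which a twitch occurs with probability 0.2 per pulse:

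- one pulse per level: accepted with probability 0.20
- any one of 5 pulses: 1 − 0.8^5 = 1 − 0.328 = 0.67
- at least 5 of 10 pulses: 0.033

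A simulation of the descending search points the same way. It assumed a threshold near 50% of output, a normal response curve with SD 1.5 to 3.5% of output, 1% steps and a start 10 points above threshold. The one-pulse rule ended on average about 1.1 to 3.1 points above threshold, and the any-of-5 rule about 1.0 to 2.3 points below. The 5-of-10 rule ended about 0.4 to 0.5 above. The one-pulse figure depends on where the search starts. These results describe the counting rule only, under assumed curves. They contain no term for thumb versus FDI, for site, or for visual versus EMG detection, and must not be read as the size of the mismatch.

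**The case against.** **The twitch rule is permitted.** Section 1 joins its two RMT definitions with an or, and Section 8 applies the first. A reader might infer that the RMT obtained is not the quantity Section 1 defines. The text does not support that: it is one of two allowed quantities. What stands is that the other cannot be used in the search as sequenced.

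**The muscle is not named.** A reader might infer that the coil is optimised for a different muscle. The documents do not identify the muscle behind the thumb twitch, they call the recorded muscle the corresponding one, and they treat the target as a single hand area. They give no distance between thumb and FDI sites. Only the narrower statement is supported: FDI response is not the search criterion.

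**The test intensity is not stated.** A floor effect requires test pulses at or near RMT. The protocol says only that the intensity is constant, so this remains an assumption. The omission also means that nothing ties the intensity to FDI.

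**The design limits the harm.** All time points within a session are compared within person, at one camera-tracked target and one intensity. An offset in site or level is shared by all of them. This objection stands in full against any claim of a false pre/post change. It does not remove added variability, or the weaker link from MEP to threshold. It also leaves session-to-session differences in RMT, although the protocol defines no formal tACS versus tRNS contrast.

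**Conclusion.** The concern holds as a weakness of measurement that is cheap to correct. It rests on the stated order of steps in Section 8, which is clear for session 1 and implied for session 2 by the similar procedure. Site and RMT are fixed by a visible twitch without a pulse count, every EMG outcome comes from FDI, and nothing later connects the two.

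The consequences are added variability, possible floor effects if test pulses are near RMT, and weaker support for two inferences: from a larger MEP to a lower threshold, and from any comparison of tACS with tRNS. None of these can be sized from the documents.

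A reader might go further and conclude that the pre/post results would be biased. The within-person comparison at one target and one constant intensity does not support that. Confidence is high on the sequence and limited on the impact.

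**What to change.** In Section 8, for both sessions:

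- connect the FDI electrodes before the hotspot search;
- define the right-hand hotspot by the FDI MEP in place of the thumb twitch;
- determine RMT with the EMG criterion already in Section 1 (above 50 microvolts in 5 of 10 trials), which also supplies the missing pulse count.

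Sections 1 and 8 would then agree on how RMT is obtained. The protocol should also state how the constant test-pulse intensity relates to the measured RMT, so that a reader can judge whether a floor effect is possible.

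The cost is a reordered step with the same electrodes and EMG pod, a few extra pulses per search, and a change of wording in Section 8.

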| APPLICATION LOCATION | Two electrodes on First Dorsal Interosseous (FDI) muscle and the reference electrode on top of the wrist (head of ulna) |
| SAMPLING FREQUENCY | 3 kHz |
| DURATION FOR EACH PULSE | 50 ms before the pulse, 200 ms after the pulse |

Transcranial altering current stimulation (tACS)

The following parameters will be applied during the tACS sessions:

| PARAMETER | DESCRIPTION/VALUE |
|----------------------|---|
| DEVICE | tES, Soterix Medical Inc. (Model: 2001) |
| FREQUENCY | 40 Hz |
| APPLICATION LOCATION | Active electrode on C3 over the right-hand area of the motor cortex and reference on the contralateral motor cortex |
| INTENSITY | 0.75 mA (1.5 mA peak-to-peak) |
| Waveform | Sinusoidal (bipolar) |
| DURATION | 10 minutes |

Transcranial random noise stimulation (tRNS)

The following parameters will be applied during the tRNS sessions:

| PARAMETER | DESCRIPTION/VALUE |
|----------------------|---|
| DEVICE | tES, Soterix Medical Inc. (Model: 2001) |
| APPLICATION LOCATION | Active electrode on C3 over the right-hand area of the motor cortex and reference on the contralateral motor cortex |
| INTENSITY | 0.75 mA (1.5 mA peak-to-peak) |
| Waveform | Random Noise (bipolar) |
| DURATION | 10 minutes |

4. Participants

This research requires a total of 50 healthy participants who must meet the following inclusion criteria:

- Between the ages of 18 years and 95 years
- MoCA score ≥ 26
- Not diagnosed with any restricting conditions such as history of seizures, epilepsy, having pacemakers, being pregnant, having a diagnosed major psychotic disorder, having pain relief medication on a daily basis, or having any metallic implants that might cause a conflict while using TMS.
- Not being on any regular nervous system medication for depression, anxiety, sleep, etc.
- Not have had any brain injury

All participants will be assessed by MoCA and will fill out the questionnaire after signing the consent form.

5. Recruitment

Potential participants will be recruited by providing a poster on the supervisor's webpage <https://home.cc.umanitoba.ca/~[name]/> and Biomedical Engineering webpage of University of Manitoba at <https://umanitoba.ca/engineering/biomedical-engineering>. Furthermore, posters will be placed around the University of Manitoba campus with permission to recruit

participants. The posters will have information about the project and an email to contact the team to participate in the study.

6. Data Analysis

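### Active MEP and cSP are compared across blocks with no control of, or account for, contraction level, so a systematic change in grip would be read as a stimulation effect

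*Combined protocol and SAP*

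**What the plan says.** Section 1 defines the active motor threshold like the resting one, "but this time while the hand is contracted". It gives no level of contraction. Section 8 sets the active state by one instruction: "the participant will be asked to gently hold the arm rest of the chair". Ten pulses are then given in that state. No force target, percentage of maximum, background EMG level, feedback or rejection rule appears anywhere.

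For the block straight after stimulation, Section 8 says "resting and active EMG will be recorded similar to the pre-tACS procedure, with 10 pulses of TMS for each of the resting and active experiments". For the last two blocks it says "A similar procedure will be followed to record the resting and active EMG after 30 minutes and after 1 hour". The tRNS session follows the same pattern, so each session has four active blocks of 10 pulses.

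Section 6 states the analysis as "The EMG recorded before and after tACS/tRNS will be compared to observe any change in the MEP". The only condition it holds fixed is TMS intensity: "while a constant amount of TMS intensity is applied to the brain before and after priming via tACS/tRNS is used". It takes a larger MEP as a sign of successful priming and a shorter cSP as a possible sign of effective preconditioning.

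The EMG table in Section 3 gives a 3 kHz sampling rate and a recording window of "50 ms before the pulse, 200 ms after the pulse". No use of the pre-pulse part is described.

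**The concern.** The plan itself treats contraction as material. Section 1 sets a different MEP criterion for each state (50 µV relaxed, 100 µV contracted), and Section 6 notes that the cSP can be seen only in an active muscle. Coil position is tracked by camera and TMS intensity is held constant, but the contraction that defines the active state is left to the participant.

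If participants grip harder or more softly on average after baseline, every active-state before/after contrast shifts, and the Section 6 reading rules attribute the shift to stimulation. The plan describes two sessions, tACS and tRNS, and no sham session, so a drift that occurs whatever is applied cannot be subtracted. If grip varies without direction, the mean change is not biased but its standard error is larger than it need be.

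**Working it through.** The plan gives n = 50 but no alpha, power, effect size or SD, so there is no stated figure to reproduce. Everything below is illustrative.

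**Inputs**
- From the documents: n = 50; 10 pulses per block; 50 ms pre-pulse window; 3 kHz sampling.
- Assumed: active MEP is proportional to (pre-pulse EMG)^b, with b = 0.3 to 1.0; grip drift ratio r = 1.1 to 1.3; block-to-block SD of log contraction s = 0.2 to 0.3; other SD of log MEP change σ = 0.4 to 0.6; paired t-test, two-sided 5%, no true effect; EMG bandwidth 400 Hz.

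**1. Shift in MEP from grip alone:** r^b − 1.
- Low: 1.1^0.3 − 1 = 3%.
- High: 1.3^1.0 − 1 = 30%.

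**2. Share of variance of the MEP change due to grip:** 2b²s² / (2b²s² + σ²).
- Low (b = 0.3, s = 0.2, σ = 0.6): 0.0072 / 0.3672 = 2%. SE inflation 1/√(1 − 0.02) = 1.01.
- High (b = 1.0, s = 0.3, σ = 0.4): 0.18 / 0.34 = 53%. SE inflation 1/√(1 − 0.53) = 1.46.

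**3. False-positive rate.** The drift in SD units is d = b·ln(r) / √(2b²s² + σ²). The rate comes from the noncentral t with 49 degrees of freedom and noncentrality d√50.

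| b | drift | s | σ | d | false-positive rate |
|---|---|---|---|---|---|
| 0.3 | 10% | 0.20 | 0.6 | 0.0286/0.606 = 0.05 | about 6% |
| 0.6 | 20% | 0.25 | 0.5 | 0.1094/0.543 = 0.20 | about 29% |
| 1.0 | 30% | 0.30 | 0.4 | 0.2624/0.583 = 0.45 | about 88% |

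For scale, the effect that 50 pairs detect with 80% power is (1.96 + 0.84)/√50 = 0.40 SD. A grip drift of that size would look the same as a detectable stimulation effect.

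**4. Sensitivity to the slope.** Fix the SD of the change in log EMG at 0.3 and take log drifts of 0.05, 0.10 and 0.20.
- b = 1.0, σ = 0.4: 11%, 28%, 79%.
- b = 0.3, σ = 0.4: 6%, 8%, 17%.
- b = 0.3, σ = 0.6: 5%, 6%, 11%.

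**5. Does adjustment work?** With b = 1.0 and σ = 0.4, 4,000 simulated trials per drift were analysed with the block-level change in log EMG as covariate. The rejection rate was 4.9% to 5.4% at every drift from 0 to 0.20. That simulation assumed no measurement error in the covariate and no effect of stimulation on it.

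**6. How well is the covariate measured?** The window holds 0.05 s × 3,000 Hz = 150 samples. The relative error of the RMS is 1/√(4 × 400 × 0.05 × number of pulses).
- One pulse: 1/√80 = 11%.
- Block of 10: 1/√800 = 3.5%.

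If the slope is estimated from pulses within a block, and true pulse-to-pulse log-grip SD is 0.1 to 0.2 (assumed), reliability is 0.01/(0.01 + 0.0125) = 0.44 to 0.04/(0.04 + 0.0125) = 0.76. About a quarter to a half of the drift would stay uncorrected. For block-level changes with s = 0.2 to 0.3, reliability is s²/(s² + 0.00125) = 0.97 to 0.99. The adjustment therefore belongs at block level.

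**The case against.** **Size.** The documents give no grip-MEP slope, grip variability or MEP SD. At the low end of the assumed ranges the problem is negligible, and the largest rates come from the steepest slope. This stands: the omission is certain, its consequence is not.

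**Likelihood of drift.** Only a systematic shift biases the mean. The task is a gentle hold for 10 pulses, with breaks, so fatigue of the grip is a weak mechanism. Section 11 lists fatigue as a possible effect of tACS/tRNS, but not fatigue of the hand. Settling in over a session of more than an hour remains possible. Drift is thus a risk that the plan cannot detect, not one shown to occur.

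**cSP.** A reader might infer that cSP is biased as much as active MEP. The documents do not support that. Section 6 says that an active muscle is needed to see the cSP, not that its duration varies with contraction level, and every figure above concerns MEP amplitude.

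**Resting MEP.** A reader might also extend the point to the resting comparison. Section 8 specifies a relaxed hand there, and the grip instruction does not apply to it.

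**Adjustment.** Pre-pulse EMG is recorded after stimulation from a muscle driven by the stimulated cortex. If stimulation changes it, adjusting removes part of a real effect. This stands, and is why adjustment should not replace the unadjusted result.

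**Priority.** Section 6 names no model, test or primary endpoint, which is a larger gap. That does not remove this one.

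**Conclusion.** The concern holds for the active-state comparisons. Contraction is set by one verbal instruction, is not matched across blocks and is absent from the analysis, while changes in active MEP and cSP are read as evidence of priming. A systematic grip change would be misattributed, and random change costs precision.

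The size cannot be determined from the documents. On the assumed ranges, grip accounts for 2% to 53% of the variance of the active MEP change, the standard error is 1.01 to 1.46 times what it could be, and the false-positive rate runs from near nominal to far above it. No single rate in that range should be quoted as the trial's error rate. For cSP the same mechanism is plausible but not quantified.

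A reader might go further and conclude that the active-state results are invalid. The text does not support that: nothing in it shows that grip will drift. The resting MEP comparison is unaffected. The change is worth making because the measure needed to check is already recorded and has no stated use.

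**What to change.** **Section 6 (analysis)**
- Compute the RMS of the 50 ms pre-pulse EMG for every active pulse. Report mean RMS by time point, with its change from baseline, for each session.
- Keep the unadjusted active MEP and cSP comparisons.
- Add a pre-specified sensitivity analysis that adjusts both for log pre-pulse RMS at block level (block mean, with or without each pulse's deviation from it). State that it estimates excitability at equal contraction, because the covariate is measured after stimulation and could be altered by it.

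**Section 8 (procedure)**
- Show the participant the live EMG trace during active blocks, so that later blocks match the baseline contraction level.

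**Cost.** One paragraph in Section 6, a few lines of code and a displayed trace; no new recordings or visits. The analysis part also works on data already collected, if the raw traces are kept. The downside is that the adjusted result could remove part of a true effect that acts through background EMG, so both results must be shown.

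Using the same window to check that the hand was relaxed in resting blocks is an optional secondary check, not part of this point.
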